11.4 Inclusion of Children, Women and Minorities

The study is open to all participants regardless of gender or ethnicity. Review of accrual to past COG studies of new agents demonstrates the accrual of both genders and all NIH-identified ethnicities to such studies. Efforts will be made to extend the accrual to a representative population, but in a Phase 1 trial which will accrue a limited number of patients, a balance must be struck between patient safety considerations and limitations on the number of individuals exposed to potentially toxic or ineffective treatments on the one hand and the need to explore gender, racial, and ethnic aspects of clinical research on the other. If differences in outcome that correlate to gender, racial, or ethnic identity are noted, accrual may be expanded or additional studies may be performed to investigate those differences more fully.

11.5 Pharmacokinetic and Correlative Studies and Response Analysis

A descriptive analysis of pharmacokinetic (PK) parameters of ramucirumab will be performed to define systemic exposure, drug clearance, and other pharmacokinetic parameters. The PK parameters will be summarized with simple summary statistics.

While the primary aim of this study is to evaluate the toxicity of ramucirumab, patients will have disease evaluations performed as indicated in [Section 8.1](#). Disease response will be assessed according to RECIST criteria for patients with solid tumors, and will be reported descriptively.

All these analyses will be descriptive in nature.

11.6 Statistical methods

11.6.1 **Analysis Sets**

Safety Analysis Set (SAS) will consist of subjects who receive any amount of study drug.

11.6.2 **Dose Evaluable Set (DES)** will consist of: 1) subjects who receive any amount of study drug and then experience DLT during Cycle 1; and 2) subjects who receive at least 85% of the prescribed dose in Cycle 1 and have an adverse event assessment in the first cycle. DES will be used for evaluation of each dose level for dose-escalation.

11.6.3 **Pharmacokinetic Analysis Set (PAS)** will include subjects who have sufficient PK data to derive at least one PK parameter.

11.6.4 **Efficacy Analyses:**

Preliminary efficacy analyses will also be performed by dose cohort for the Safety Analysis Set. Data cut-off for primary study analysis will occur when all enrolled subjects have completed 6 cycles of treatment or discontinued study drug administration. After the final analysis, additional analyses may be performed as appropriate.

11.6.5 **Pharmacokinetic Analyses**

Serum concentrations of Ramucirumab will be tabulated and summarized by dose level and time. Ramucirumab PK parameters will be derived from serum concentrations by non-compartmental analyses using actual times. Minimally, the following PK parameters will be calculated: C_{max} , t_{max} , and $AUC (t_{1/2}, CL, and Vd_{ss})$ will be calculated only if the data permit). Additional analysis utilizing the population pharmacokinetic approach may also be conducted if deemed appropriate.

11.6.6 **Immunogenicity Analyses**

Immunogenicity incidence will be tabulated, and correlation of immunogenicity to ramucirumab drug level, activity, and safety will be assessed as appropriate.

11.6.7 **Statistical Analyses**

Baseline demographics and baseline disease characteristics will be summarized for all enrolled patients who had at least one dose of study therapy.

Listing of patients including those treated at the MTD will be generated.

Treatment-emergent CTCAEs will be summarized by each dose level and for

THIS PROTOCOL IS FOR RESEARCH PURPOSES ONLY, SEE PAGE 1 FOR USAGE POLICY

overall population by each CTCAE grade separately.

Best overall response, duration of response, and duration of stable disease will also be summarized descriptively by each dose level.

Listing of deaths on study or 30 day post-discontinuation will be provided. Listing of SAEs will also be produced. Listing of AEs leading to treatment discontinuation will be provided.

CTCAEs possibly study drug related or regardless of causality will be presented separately.

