The animal toxicology studies of ramucirumab were conducted in cynomolgus monkeys. A tissue cross-reactivity study was conducted with a full panel of cynomolgus monkey and human tissues that showed that the tissue reactivity of ramucirumab observed in both tissues was similar, indicating that the cynomolgus monkey is an appropriate animal model for toxicity testing of ramucirumab. In a 5-week, 4-dose study, cynomolgus monkeys were given ramucirumab I.V. weekly at dose levels 0, 4, 12, or 40 mg/kg on Days 1, 15, 22, and 29, with a subset of monkeys sacrificed after the last dose and a second subset of monkeys entering a 6-week recovery phase for toxicity assessments. The only significant findings were mild local injection site reactions. I.V. administration was well tolerated at all dose levels and the no-observable adverse effect level was 40 mg/kg, the highest dose administered. A second toxicology study assessed the long-term (chronic) administration of ramucirumab in cynomolgus monkeys who received doses of 0, 5, 16, or 50 mg/kg administered intravenously every week for 12 or 39 weeks. The results revealed nephrotoxicity consistent with multi-focal and marked glomerulonephritis in both kidneys in monkeys receiving doses of 16 and 50 mg/kg for 39 weeks. In addition, secondary changes were also observed in the tubules, collecting ducts and the renal interstitium. Osteochondropathy and thickening of the epiphyseal growth plate was noted at all doses administered.⁴⁸

In addition to toxicology studies, a wound healing study following a single dose of ramucirumab was also conducted at doses 5, 15, and 50 mg/kg since there is a strong role for VEGF pathway in wound healing. This study did not reveal a clinical or histological impairment of wound-healing in this cynomolgus monkey linear incision model after a single dose.⁴⁸

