5.0 TREATMENT PROGRAM

5.1 Overview of Treatment Plan

Treatment Schedule Table		
Day	Ramucirumab (i.v. over 60 minutes)	Disease Evaluation
1	X	
15	X	

THIS PROTOCOL IS FOR RESEARCH PURPOSES ONLY, SEE PAGE 1 FOR USAGE POLICY

29	X	
42		X

A cycle of therapy is considered to be 42 days. A cycle may be repeated for a total of 8 cycles, up to a total duration of therapy of approximately 12 months. This is an open-label study.

Effort should be made to begin protocol therapy on Monday through Thursday if possible to accommodate correlative sample shipments.

Drug doses should be adjusted based on actual weight measured within 7 days prior to the beginning of each cycle.

Update: With the release of Amendment #2A, the dose escalation portion of the study is complete. Given this, Part B will open to patients with relapsed or refractory CNS tumors.

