10.0 CRITERIA FOR REMOVAL FROM PROTOCOL THERAPY AND OFF STUDY CRITERIA

10.1 Criteria for Removal from Protocol Therapy

- a) Clinical (including physical examination or serum tumor markers) or radiographic evidence of progressive disease (See [Section 12.0](#)).
- b) Adverse Events requiring removal from protocol therapy (See [Section 6.0](#)).
- c) Refusal of protocol therapy by patient/parent/guardian
- d) Non-compliance that in the opinion of the investigator does not allow for ongoing participation.
- e) Completion of 8 cycles of therapy.
- f) Physician determines it is not in the patient's best interest.
- g) Repeated eligibility laboratory studies (CBC with differential, bilirubin, ALT (SGPT) or serum creatinine) are outside the parameters required for eligibility prior to the start of ramucirumab (See [Section 8.1](#)).
- h) Study is terminated by Sponsor.
- i) Pregnancy

Patients who are removed from protocol therapy during cycle 1 should continue to have the required observations in [Section 8.1](#) until the originally planned end of the cycle or until all adverse events have resolved per [Section 13.4.4](#), whichever happens LATER. The only exception is with documentation of the patient's withdrawal of consent. Patients who are removed from protocol therapy in subsequent cycles should have the necessary observations to ensure adequate clinical care.

Patients who are off protocol therapy are to be followed until they meet the criteria for Off Study (see below). Ongoing adverse events, or adverse events that emerge after the patient is removed from protocol therapy, but within 30 days of the last dose of investigational agent, must be followed and reported via RAVE and CTEP-AERS (if applicable). Follow-up data will be required unless consent is withdrawn.

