APPENDIX IV: IMMUNOGENICITY FORM: ANTI- RAMUCIRUMAB ANTIBODY STUDIES

COG Pt ID # _____ ACC # _____

Please do not write patient names on this form or on samples.

Cycle 1, Day 1 Date: ____/____/____

Weight: _____ kg Dose Level: _____ mg/kg Total Dose: _____ mg

Sample Collection: Blood samples (2.5 ml) will be obtained at the time points listed in the table below. Record the exact date and time each sample is drawn and the time of the ramucirumab administration. If this form will be used as a source document, the site personnel who collected the samples or research staff responsible for the research specimen must initial in the table below, next to the respective sample.

Blood Sample No.	Time Point	Scheduled Sample Collection Time	Scheduled Ramucirumab Time Point	Date Sample Collected or Dose Given	Time Sample Collected or Dose Given (24-hr clock)	Staff Initials
1	Cycle 1, Day 1	Prior to infusion		/ /	____:____	
			Cycle 1, Day 1	/ /	Start time ____:____	
2	Cycle 1, Day 15	Prior to infusion		/ /	____:____	
			Cycle 1, Day 15	/ /	Start time ____:____	
3	Cycle 1, Day 29	Prior to infusion		/ /	____:____	
			Cycle 1, Day 29	/ /	Start time ____:____	
4	Cycle 3, Day 1	Prior to infusion		/ /	____:____	
			Cycle 3, Day 1	/ /	Start time ____:____	
5	Cycle 5, Day 1	Prior to infusion		/ /	____:____	
			Cycle 5, Day 1	/ /	Start time ____:____	
FOLLOW-UP: Date of last dose of Ramucirumab: ____/____/____ Cycle # _____						
Blood Sample No.	Scheduled Sample Collection Time			Date Sample Collected	Time Sample Collected (24-hr clock)	
6	~30 days after last dose of ramucirumab			/ /	____:____	

In the event an infusion-related reaction is experienced, an additional blood sample for PK and Immunogenicity will be collected as close to the onset of the infusion-related reaction, at the time of its resolution, and approximately 30 days after resolution of the event.

Blood Sample No.	Time Point	Scheduled Sample Collection Time	Date of IRR Onset/Resolution	Date Sample Collected	Time Sample Collected or Dose Given (24-hr clock)	Staff Initials
IRR-1	Onset of IRR	unscheduled	/ /	/ /	____:____	
IRR-2	Resolution of IRR	unscheduled	/ /	/ /	____:____	
IRR-3	~30 Days Post-Resolution	unscheduled		/ /	____:____	

Sample Processing Procedures: Refer to manual for sample processing and shipping details.

One copy of this Immunogenicity Study Form should be uploaded into RAVE. See manual for detailed guidelines for packaging and shipping Immunogenicity samples to Covance.

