### 6.7.1. Extent of Exposure

The following exposure-related variables will be reported:

- **Cumulative dose (mg/kg)** is calculated as sum of all calculated dose levels, where calculated dose level (mg/kg) = (actual total dose [mg]) / (closest body weight [kg] prior to the treatment).
- **Duration of treatment (week)** is calculated as (date of last dose in last cycle – date of first dose + 14)/7.
- **Dose intensity (mg/kg/week)** is calculated as cumulative dose / duration of treatment.
- **Relative dose intensity (%)** is calculated as dose intensity / planned dose intensity \* 100.

The following analyses on the defined reexposure-related variables will be performed using summary statistics (number of patients, mean, and standard deviation) by dose group:

- Exposure: duration of treatment, number of cycles received, number of patients who received  $\geq 1$  cycle,  $\geq 2$  cycles, ...,  $\geq 8$  cycles; and cumulative dose.
- Dose adjustment: number of patients with dose adjustments: dose reduction, dose omission and dose delay; reason for dose adjustments.

- Dose intensity: weekly dose intensity, relative dose intensity.

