### 6.7.2. Adverse Events

**Adverse events** are defined as any untoward medical occurrence in a patient administered a pharmaceutical product, without regard to the possibility of a causal relationship.

**Treatment-emergent adverse events (TEAE)** is defined as any untoward medical occurrence that either occurs or worsens at any time after treatment baseline and that does not necessarily have to have a causal relationship with this treatment.

**Serious adverse events (SAE)** are defined as any of the AEs that results in one of the following outcomes:

- death
- initial or prolonged inpatient hospitalization
- a life-threatening experience (that is, immediate risk of dying)
- persistent or significant disability/incapacity
- congenital anomaly/birth defect considered significant by the investigator
- considered significant by the investigator for any other reason based upon appropriate medical judgement

A summary overview of all AEs will be provided per study arm. The overview will tabulate number of subjects with:

- at least 1 TEAE
- at least 1 CTCAE grade  $\geq 3$  TEAE
- at least 1 serious AE
- discontinuation from study treatment due to AE
- discontinuation from study treatment due to SAE
- death due to AE on study treatment
- death due to AE within 30 days of last infusion or discontinuation from study treatment

The summary will be provided regardless of study drug causality, and repeated for events deemed by investigator to be possibly related to study medication.

The following summaries of TEAEs by treatment dose levels will be provided (\*repeated for events deemed by the investigator to be possibly related to study medication)

- by PT \*
- by maximum CTCAE grade and by SOC and PT

Consolidated AE may be summarized for TEAE and study treatment-related TEAE. A patient listing of all AEs will be provided.

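### The 6-cycle primary data cut-off can fall before the last-enrolled patients' 30-day post-dose data, and before cycles 7 and 8 if they are still on drug

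*Protocol*

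**What the plan says.** Protocol 11.6.4 states the trigger: "Data cut-off for primary study analysis will occur when all enrolled subjects have completed 6 cycles of treatment or discontinued study drug administration". It adds only that further analyses are optional once the final analysis is done. It does not say how the final analysis differs from the primary one, or when its data close.

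Treatment can last longer than that trigger. Protocol 5.1 says "A cycle may be repeated for a total of 8 cycles, up to a total duration of therapy of approximately 12 months", and among the removal criteria in 10.1 is "Completion of 8 cycles of therapy". Follow-up lasts longer still. Under 10.1, adverse events are followed and reported to 30 days after the last dose, and 10.2 takes patients off study at that point.

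Several planned outputs and samples depend on that later period:

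- Protocol 11.6.7 lists deaths on study or within 30 days of discontinuation. SAP 6.7.2 tabulates "death due to AE within 30 days of last infusion or discontinuation from study treatment", and SAP 6.7.3 summarises deaths within and beyond 30 days.
- SAP 6.7.4 takes the worst laboratory grade up to 30 days after discontinuation.
- SAP 6.7.1 plans "Exposure: duration of treatment, number of cycles received, number of patients who received" each number of cycles, up to at least 8.
- Appendix IV places the last antibody sample about "30 days after last dose of ramucirumab". Appendices III and V-A do the same for PK and plasma markers.
- In the Protocol 8.1 schedule, the echocardiogram or radionuclide study appears only before the study and at the visit 30 days after the last dose.

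SAP 6.5.1 refers to a data-inclusion cut-off date in its PFS and OS censoring rules, but the SAP never defines it.

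**The concern.** Describing toxicity (1.1.3), characterising immunogenicity (1.1.4) and judging tolerability in CNS tumors (1.1.2) are all primary aims. A cut-off that closes before a patient's 30-day point can remove late events from the primary tables, and an event left out can only lower the count.

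For a patient who passes Cycle 5 Day 1, the 30-day sample is the only scheduled antibody sample after that day. It is also the only one after the final dose. On the 8.1 schedule, the 30-day visit carries the only planned cardiac measurement after baseline, and Protocol 2.1 names cardiotoxicity as being of particular interest in children.

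The patients at risk are the last enrolled. Part B opens only after Part A has set the RP2D (5.3.2), so these are likely to be mainly the CNS cohort, which is small.

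**Working it through.** **Inputs.** "A cycle of therapy is considered to be 42 days" (5.1), with doses on days 1, 15 and 29 of each cycle (5.1). Follow-up ends 30 days after the last dose (10.1, 10.2). Accrual is 1 to 2 patients per month (11.1). Planned enrolment is 29 in Part A and 8 in Part B (11.1), so 29 + 8 = 37. A month is taken as 30.4375 days, and cycles are assumed to run on schedule.

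**The plan's own figure.** 8 × 42 = 336 days, and 336 / 30.4375 = 11.0 months. To the end of follow-up it is 353 days, or 11.6 months. Both agree with the stated duration of approximately 12 months.

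**Calendar for one patient.** Cycle k ends on day 42k. Its last dose is on day 42(k − 1) + 29, and the 30-day point is 30 days after that.

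| Stops after | Last dose | Cycle ends | 30-day point | Days after day-252 cut-off |
|---|---|---|---|---|
| Cycle 6 | 239 | 252 | 269 | 17 |
| Cycle 8 | 323 | 336 | 353 | 101 |

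Suppose the last-enrolled patient reaches the end of cycle 6, which triggers the cut-off on that patient's day 252.

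- If dosing stops there, 252 − 239 = 13 days have passed since the last dose. So 30 − 13 = 17 of the 30 follow-up days, and the final samples, come after the cut-off.
- If dosing goes on to cycle 8, then 353 − 252 = 101 days come after it, including 6 of that patient's 24 doses and all of the 30-day follow-up.

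If the triggering patient stops earlier, the cut-off is the discontinuation date. With discontinuation recorded 0 to 14 days after the last dose, 30 − 14 = 16 to 30 − 0 = 30 follow-up days are missed. The exception is a discontinuation recorded 30 or more days after the last dose, for example after a long hold.

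**How many patients.** The cut-off is one date for the whole trial. A patient starting s days before the last one reaches the end of follow-up no later than day 353 − s on the last patient's calendar. That exceeds 252 only if s is below 101.

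- 101 / 30.4375 = 3.32 months.
- At 1 per month: 3.3 patients, and 3.3 / 37 = 9%.
- At 2 per month: 6.6 patients, and 6.6 / 37 = 18%.
- If all of them are in Part B: 3.32 / 8 = 41% to 6.64 / 8 = 83% of its 8 planned patients.

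These are ceilings on who could be affected, because most require treatment past cycle 6. If the last-enrolled patient stops early, the cut-off comes sooner and the group at risk shifts to somewhat earlier starters.

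**What is not touched.** DLTs are counted in cycle 1 (5.5, 11.2.2). The RP2D rule uses the trough at day 42 (2.5, 11.2.3). The last on-treatment antibody sample, Cycle 5 Day 1, is on day 4 × 42 + 1 = 169.

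**The case against.** The best defence is that 11.6.4 names two analyses: a primary one with this cut-off and a later final one. SAP section 3 also refers to a final analysis. On that reading the 6-cycle cut-off is an early read-out and the complete tables belong to the final analysis. In addition, the sentence sits under the efficacy heading, and the SAP's safety outputs carry no cut-off. They could therefore be meant to cover full follow-up.

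This reading is possible, but the text does not secure it. The final analysis has no cut-off and is never distinguished from the primary one. The sentence speaks of the primary study analysis, not of efficacy alone. If it did apply only to efficacy, safety and immunogenicity would have no stated cut-off at all, and that would need the same sentence to repair.

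Three parts of the defence stand. The data are still collected: follow-up to 30 days is required, expedited reporting continues, and the monitoring committee meets at least every 6 months. Only a few late starters can be affected. The dose-finding decisions do not depend on this cut-off.

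**Conclusion.** The point holds as a gap in the completeness of the primary safety and immunogenicity analysis. It is worth correcting, but it does not threaten the dose decision. Followed as written, the rule can leave 17 to 101 days of a last-enrolled patient's course outside the primary analysis if that patient completes 6 cycles. If the triggering patient stops sooner, usually 16 to 30 days of follow-up are left out. The planned 30-day death listing, laboratory shifts, end-of-therapy echocardiogram and antibody incidence would then be incomplete. The ceiling is roughly 3 to 7 of 37 patients, probably mainly in Part B. This assumes on-schedule cycles, 1 to 2 patients per month, planned enrolment without the expansions allowed in 11.1, and a last-enrolled patient who reaches cycle 6. Early stopping lowers it.

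A reader might infer three stronger things that the documents do not support:

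- That the late data are lost. They are collected; what is not assured is their place in the primary analysis.
- That a quarter of treatment time is excluded. The share (6 of 24 doses, or 12 of 48 weeks) applies only to a patient who starts last and completes all 8 cycles. Patients who started well before the last one have cycles 7 and 8 inside the cut-off.
- That a 36-week cut-off (6 × 42 / 7) just misses a known toxicity, because Protocol 2.2.2 reports "glomerulonephritis in both kidneys in monkeys receiving doses of 16 and 50 mg/kg for 39 weeks". Those animals were dosed weekly, not every two weeks, and no onset time is given. Earlier-enrolled children can also pass 39 weeks before the cut-off.

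**What to change.** In Protocol 11.6.4, state that the cut-off for the primary safety and immunogenicity analysis is the date on which every patient has both (a) completed 8 cycles or discontinued study drug and (b) reached the point 30 days after the last dose or otherwise gone off study. Define the SAP's data-inclusion cut-off date in the same words. If a 6-cycle read-out is wanted, keep it, label it interim, and say which outputs it covers.

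The cost is one sentence in each document. Dosing, visits and samples do not change. On schedule, the read-out moves later by at most about 101 days (day 252 to day 353 of the last patient). If no late patient is treated past cycle 6, it moves by no more than about 30 days.

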12.0 EVALUATION CRITERIA

12.1 Common Terminology Criteria for Adverse Events (CTCAE)

The descriptions and grading scales found in the revised NCI Common Terminology Criteria for Adverse Events (CTCAE) version 5.0 will be utilized for AE reporting. All appropriate treatment areas should have access to a copy of the CTCAE version 5.0. A copy of the CTCAE version 5.0 can be downloaded from the CTEP web site http://ctep.cancer.gov/protocolDevelopment/electronic_applications/ctc.htm.

12.1.1 Adverse Event (AE or Adverse Experience): Any untoward medical occurrence associated with the use of a drug in humans, whether or not considered drug related. Therefore, an AE can be ANY unfavorable and unintended sign (including an abnormal laboratory finding), symptom, or disease temporally associated with the use of a medicinal (investigational) product, whether or not considered related to the medicinal (investigational) product (attribution of Unrelated [“unrelated”, “unlikely”] or Related [“possible”, “probable”, or “definite”]). (International Conference on Harmonisation [ICH] E2A, E6).

12.1.2 All AEs for which a CTCAE term exists must be reported routinely as outlined in the protocol (see [Section 13.5](#)). All Serious AEs (as defined in [Table A](#) in [Section 13.1](#)) must be reported expeditiously. For detailed AE reporting guidelines refer to the “NCI Guidelines for Investigators: Adverse Event Reporting Requirements for DCTD (CTEP and CIP) and DCP INDs and IDEs”: http://ctep.cancer.gov/protocolDevelopment/adverse_effects.htm.

